of main importance for sleep apnoea monitoring: namely the “I”, “J” and “K” waves (7, 8). These waves are elicited by the ventricular contraction which occurs after the QRS complex on the ECG. They represent the body movements in response to the cardiac blood ejection (22). Should the thoracic aorta be simplified into an ascending and a descending tube, on whom blood pressure and volume flow rate forces act in opposite directions, then the BCG waveforms represents the sum of those forces (8). Various cardiovascular parameters can be estimated from the BCG signal, and are shortly presented below. The J wave of the BCG represents the point of highest amplitude in the BCG waveform; heart rate can be determined by the time interval between consecutive J peaks, the J-J intervals (23). Various algorithms can assess heart rate from BCG signals (24-28). Also, heart rate variability, a non-invasive tool to assess cardiac sympathetic and parasympathetic modulation (29), can be calculated from BCG peak intervals, without the need of RR interval calculations obtained from ECG recordings. Changes in BCG waveforms amplitude are related to stroke volume (SV) and cardiac output (CO) modifications in healthy subjects (30, 31). Finally, similarly to SCG, BCG measurements provide an estimation of the PEP (32, 33), and the LVET which indicates the percentage of the cardiac cycle devoted to ejection as compared to ventricular filling (34, 35).

Sleep disordered breathing and their cardiovascular impact: why detect them?

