Group A. After a fine tuning period of the KCG signal post processing to maximise the sensitivity and specificity of voluntary apnoea detection in health subjects, we will start the first validation study. In 46 healthy volunteers, a computer program will generate random instructions of periods of normal breathing, voluntary end-expiratory breathing cessations periods (as surrogate of central apnoea) and Muller's manoeuvre (as surrogate of obstructive apnoea). Meanwhile, the KCG will record the above-mentioned parameters. The number and duration of voluntary central and obstructive apnoea will be assessed in the KCG recordings, not knowing how many were actually generated by the computer program. We will also record the ECG, heart rate, beat to beat non-invasive blood pressure (Finometer), humeral blood pressure (Dinamap), ventilation, end-tidal CO₂ (AD instruments), O₂ saturation (Nellcor), cardiac output (CO) (Philips).

Group B. In patients suspected of sleep apnoea and admitted to the sleep unit of the Erasme hospital to perform sleep test as required by their medical condition, we will simultaneously record KCG and PSG and qualitatively compare the data. Bland-Altman plots will analyse the agreement between the sleep recordings obtained with the two methods. Peculiar attention will be paid to the accuracy of the detection of obstructive *versus* central *versus* mixed apnoea, of awakenings, and of the time spend in bed. In this second phase of the study, we plan to record these parameters only in selected patients, who will not disclose marked abnormalities which could hamper the reliability of the KCG recordings, namely moderate or severe valvular disease, permanent atrial fibrillation or frequent premature contractions, atrio-ventricular conduction disturbances, medications which reduce heart rate and heart rate variability (beta blockers, anti-arrhythmic drugs, calcium blockers, ...), cardiac rhythm driven by a pace maker, heart failure of any origin, neurological diseases responsible for abnormal movements (restless leg syndrome, Parkinson disease, ataxia ...).

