Group C. In patients with a diagnosis of OSA, we will determine if KCG is capable to reliably assess the efficacy of the nCPAP therapy in comparison to simultaneous PSG recording. Ongoing adjustment in CPAP therapy pressure during the night, and its effect on cardiovascular haemodynamic assessed by the KCG, will be taken into account as well. The capability of the technique to detect changes in sleep quality will be tested both *within* subjects (before vs. after nCPAP therapy in the same patient) as well *among* the subjects investigated. The same restriction in the recruitment of the subjects of group B will be applied for the present group.

Group D. After validation of the three previous steps, we plan to extend the recordings on 100 unselected consecutive patients who will undergo PSG recordings because of complains of sleep apnoea. This will validate the clinical usefulness of KCG recording for the detection of sleep apnoea even in patients with multiples co-morbidities.

2-SECONDARY HYPOTHESES

We will test the hypothesis that the apnoeic events profoundly affected the KCG signals (PEP, LVET and PEP/LVET ratios). These parameters are affected by changes in cardiac pre- and after- load and sympathetic activity on myocardial contractility. Similarly, we plan to test the hypothesis that the isovolumic relaxation time (IVRT), an index of diastolic performance during the cardiac cycle, will be altered during the obstructive apneas, because marked variation in intrathoracic pressure result in large increases in LV transmural gradient and thereby reduce LV compliance. CPAP therapy should markedly reduce the nighttime variability in these parameters.

We will also asses the R-J interval which is related to blood pressure and determine if this parameter rises during the apneas and arousals when sympathetic activity is increased. Determination of the J-J intervals and the corresponding HRV, which is under strong autonomic control, should also present distinct changes in OSA patients, as compared to subjects receiving efficacious nCPAP therapy.

Last, breathing effort variations will be assessed. This refers to the mechanical interaction between respiration and KCG signals when sleep apnea occurs, independently from an autonomic nervous modulation of heart rate variability: when the obstructive apneic event occurs, the airflow decreases, which result in a

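### HRV from J-J intervals is read as autonomic, but J-J also carries beat-to-beat R-J variation that may differ between untreated OSA and nCPAP, by an unknown amount and in an unknown direction

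*Protocol*

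**What the plan says.** The background on SCG and BCG signals in the Protocol says that "heart rate can be determined by the time interval between consecutive J peaks, the J-J intervals". It adds that HRV "can be calculated from BCG peak intervals, without the need of RR interval calculations obtained from ECG recordings".

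Under Secondary Hypotheses in section 2 this becomes a planned comparison: "Determination of the J-J intervals and the corresponding HRV, which is under strong autonomic control, should also present distinct changes in OSA patients", the contrast being "as compared to subjects receiving efficacious nCPAP therapy". The sentence before it reads: "We will also asses the R-J interval which is related to blood pressure and determine if this parameter rises during the apneas and arousals".

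The paragraph before that concerns systolic timing: "We will test the hypothesis that the apnoeic events profoundly affected the KCG signals (PEP, LVET and PEP/LVET ratios"). After adding the isovolumic relaxation time, it predicts that "CPAP therapy should markedly reduce the nighttime variability in these parameters".

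The ECG is listed explicitly for Group A ("We will also record the ECG, heart rate, beat to beat non-invasive blood pressure (Finometer"). For patients, an R wave is implied by the R-J measurement, but the text names no HRV computed from R-R intervals. It gives no HRV index, no HRV standard deviation and no size for any R-J change.

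**The concern.** J-J HRV equals R-R HRV only when R-J hardly changes from beat to beat. R-J reflects mechanical and pressure timing as well as neural drive. The protocol expects timing of this kind to be disturbed in untreated OSA and to settle on nCPAP. If beat-to-beat R-J variation behaves in the same way, J-J HRV carries a component that is not heart-rate modulation and whose size changes with the condition under comparison. That is differential measurement error, not background noise common to both sides.

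At stake is the interpretation. A J-J HRV difference between OSA and nCPAP could be credited to autonomic control when R-R variability had not changed, or a real R-R difference could be masked. The Perspectives section wants KCG to show the cardiovascular consequences of sleep apnoea and of nCPAP, so the attribution matters even for a secondary measure.

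**Working it through.** There is no figure in the protocol to reproduce. Every millisecond value below is an assumption, used only to show the range.

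**Identity.** JJ(n) = RR(n) + RJ(n+1) − RJ(n). Hence Var(JJ) = Var(RR) + Var(ΔRJ) + 2·Cov(RR, ΔRJ). The successive difference of JJ, which RMSSD uses, gains RJ(n+2) − 2RJ(n+1) + RJ(n).

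**1. Sustained shift.** ΔRJ is zero except at the transition beats, so the shift cancels.

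**2. Smooth cyclic shift, R-R independent of R-J.** Assume 40 ms peak to peak (amplitude 20 ms) over 40 beats.
- The second difference has amplitude 20 × 4·sin²(π/40) = 0.49 ms, mean square 0.12 ms². RMSSD of 30 ms becomes √(900 + 0.12), about +0.01%.
- ΔRJ has amplitude 20 × 2·sin(π/40) = 3.14 ms, variance 4.92 ms². An R-R SD of 30 ms becomes √904.92 = 30.08 ms (+0.3%); an SD of 50 ms rises 0.1%.

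**3. Abrupt step, R-R independent of R-J.** Assume 40 ms up and 40 ms down once per 40 beats. Var(ΔRJ) = 2 × 1600/40 = 80 ms². An SD of 30 ms becomes √980 = 31.3 ms, about +4.4%. A 20,000-beat simulation gave +4.5% for SD and about +12% for RMSSD. This was the largest such case among steps of 5 to 40 ms and R-R SDs of 30 to 80 ms.

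**4. Breath-rate swing, uncorrelated with R-R.** With amplitude A and P beats per breath, RMSSD² gains [A·4·sin²(π/P)]²/2.

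| A, P | Gain in RMSSD² | RMSSD 20 ms | RMSSD 30 ms |
|---|---|---|---|
| 5 ms, 5 beats | 23.9 | +2.9% | +1.3% |
| 5 ms, 4 beats | 50 | +6.1% | +2.7% |
| 10 ms, 5 beats | 95.5 | +11.3% | +5.2% |
| 10 ms, 4 beats | 200 | +22.5% | +10.6% |

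**5. Independent beat-to-beat R-J noise of SD s.** The variance gains 2s². RMSSD² gains (1 + 4 + 1)s² = 6s².
- RMSSD 20 ms: s = 2, 5, 10 ms gives +3.0%, +17.3%, +58.1%.
- RMSSD 40 ms: +0.7%, +4.6%, +17.3%.
- SD of intervals at s = 10 ms: √(30² + 200) = 33.2 ms (+10.6%) for an SD of 30 ms; +1.6% for an SD of 80 ms.

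**6. Sign.** Take case 2 with R-R SD 30 ms and a slow R-R component in step with ΔRJ, of amplitude 0.8 × 30 × √2 = 33.9 ms. The covariance term is ±33.94 × 3.138 = ±106.5 ms². The SD becomes √(900 + 106.5 + 4.9) = 31.8 ms (+6.0%) or √(900 − 106.5 + 4.9) = 28.3 ms (−5.8%). With the abrupt step and correlated R-R, simulation reached +11.4%.

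The same holds at breathing rate. Take RMSSD 30 ms with half of RMSSD² (450) at that rate, and the R-J swing of 5 ms at 4 beats per breath (50). Full correlation gives 900 + 50 ± 2√(450 × 50) = 1250 or 650, so RMSSD becomes 35.4 ms (+18%) or 25.5 ms (−15%).

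**The case against.** The strongest reply is that the R-J hypothesis concerns a rise over an event, and an event-length rise almost vanishes from J-J (cases 1 and 2). This stands. A reader might infer that an R-J shift in itself adds variability to J-J; the arithmetic shows otherwise. The large percentages in case 5 need independent beat-to-beat noise, which the protocol does not hypothesise. A reader might also expect slow R-J drift to load mainly on low-frequency HRV. That is not supported either: differencing attenuates slow change, with a gain of 2·sin(π/40) = 0.16 at a 40-beat cycle.

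Second, a reader might infer that the bias favours the hypothesised result. The documents do not support this. The protocol predicts distinct changes without a direction and names no index, and covariance with R-R can lower J-J variability. The absence of a direction does not clear the plan, however: distortion either way could pass as support or hide a real change.

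Third, J-J HRV is a legitimate KCG parameter to study, the autonomic clause can be read as rationale, and the background sentence on dispensing with R-R intervals describes what BCG can do. Index choice and artefact handling may sit in an SAP that is not shown. All fair. What remains is what the protocol itself fixes: J-J as the source of HRV and autonomic control as its reading, beside its own expectation that cardiac timing will vary differently in the two conditions.

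**Conclusion.** The point holds as a possible contamination, not a demonstrated bias. J-J HRV mixes R-R variability with beat-to-beat R-J variation, and the protocol's own hypotheses give reason to expect the mix to differ between untreated OSA and nCPAP. J-J HRV alone therefore cannot carry the autonomic reading.

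The size is unknown because the protocol gives no R-J variation. On the assumptions above it is negligible for sustained or smooth slow shifts, about 1% to 22% of RMSSD for uncorrelated breath-rate swings of 5 to 10 ms amplitude, and up to 58% for independent noise of SD 10 ms on an RMSSD of 20 ms. The direction is also unknown.

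The effect is confined to a secondary hypothesis. Apnoea detection against polysomnography and the group sizes do not depend on it. The change is worth making mainly because it costs so little.

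**What to change.** In the secondary hypotheses, state that HRV for the autonomic hypothesis is computed from the R-R intervals of the ECG that the R-J interval already requires. Keep J-J HRV as the KCG device measure. Report the agreement between J-J and R-R HRV, together with the variance of the beat-to-beat R-J change, separately for event (apnoea or arousal) and event-free segments and by nCPAP status. Interpret a J-J difference as autonomic only where R-R HRV shows it too.

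Cost: a change of wording and one further computation on R peaks that must be detected anyway for R-J. It needs no new recording, and no group size changes. Since the ECG is named explicitly only for Group A, a sentence confirming that R peaks are available in the patient recordings would complete the change.

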Sleep apnoea syndrome is a common chronic respiratory disease characterised by cyclic airflow cessations during sleep. Clinically, they are classified in three entities: obstructive, where the airflow cessation is due to upper airways collapse; central, where the airflow cessation arise from a central lack in driving to the breathing muscles with no compensatory respiratory efforts; mixed, characterised by an initial central event followed by an obstructive one. Nowadays, up to 24% of men and to 9% of women aged 30 to 60 years disclose already an asymptomatic and underdiagnosed sleep disorder breathing (SDB) (36). Its current high prevalence will supposedly increase in the future years, as a result of the obesity pandemic in an ageing population. SDB is a potential cardiovascular risk factor (37). A patent causal relationship between SDB and cardiovascular disease has not been clearly established until now, but several chronic patho-physiological mechanisms could make sense in supporting such a link. Intermittent hypoxaemia, due to cycled upper airway collapse, is responsible for abnormal sympathetic activation (38), endothelial dysfunction (39), oxidative stress (40) and inflammation (41), all of which are related to cardiovascular illnesses, especially hypertension (42), atherosclerosis (43), cardiac arrhythmias (44), heart failure (45), and coronary artery disease (46). SDB is, likewise, positively correlated with an increased morbidity and mortality in the cardiovascular population (47, 48) and seems to be an independent predictive factor in cardiovascular mortality after an acute coronary syndrome (49).

Moreover, the classical profile of patients at risk of having SDB (obese subjects, Pickwickian syndrome) has changed in the past year, so that there are new categories of patients who should be evaluated for sleep apnoea, above all those with cardiovascular co-morbidities (50).

Sleep disordered breathing and kino-cardiography: a new and promising tool for unobstrusive recording of SDB and its impact on the cardiovascular system.

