- 3) The unique expertise of our research team is that we are capable to record SCG and BCG signals in 3 dimensions (57, 58), both linearly and rotationally (16-18). While the above mentioned studies (52-56) assessed BCG changes only in a horizontal plane (x and y axis), which is not representative of the complex cardiac mechanic, we are capable to record these changes in a third anteroposterior dimensions (z axis). This is important because of the anterior-posterior direction of the aortic arch. In addition, as emphasized in the introduction of this research proposal, an important component of the body reaction to the heart movements is rotational, which we are capable to record in 3 dimensions. Overall the combined SCG and BCG 3D-linear and 3D-rotational signals represent 6 degrees of freedom (DOF) while past BCG had only 2-DOF. For simplicity, this 6 DOF signal combination will be designated as Kino-cardiography (KCG) recordings in this research proposal. We anticipate that the unique KCG properties will considerably increase our detection capability of obstructive and central apnoea, as compared to previous studies.

2. Aims and hypothesis tested

The main hypothesis tested in our study is that KCG provides sensitive and accurate measures of obstructive and central apnoea as compared to state-of-the-art polysomnography. Our secondary hypotheses are related to modifications in the SCG and BCG parameters during the apnoea and the effects of nCPAP therapy: we believe that the KCG signals are profoundly affected by the apnoea and they are reversed to the normal baseline with the CPAP. These hypotheses will be tested through a series of studies in normal volunteers and patients.

1-MAIN HYPOTHESES:

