breathing effort thereafter. We will test the hypothesis that these respiratory abnormalities are readily detectable by the KCG.

3. Methods

Study design and recruitment, expertise of the research group

Study A is an interventional pre-study on voluntary breath holding on healthy subjects. The parameter taken into consideration for sample size calculation in this group is the total (linear and rotational) systolic kinetic energy of the SCG (S_{sys_kin}) and the rolling ratio between the mean value and the standard deviation of this parameter: $H = \text{Mean}(S_{sys_kin}) / \text{Std}(S_{sys_kin})$. H discriminated voluntary obstructive apneas from episodes of normal respiration in a healthy volunteer ($H = 1.1627$ and 0.2308 , respectively). The sample size is determined according to: $2 \cdot (Z_{\alpha} + Z_{1-\beta})^2 \cdot \sigma^2 / \Delta^2$, where $\alpha = 5\%$ is the accepted error, leading to $Z_{\alpha} = 1.96$ (2-sided); $\beta = 95\%$ is the power of the study, leading to $Z_{1-\beta} = 1.64$; σ is the estimated standard deviation of H; Δ is the estimated effect of obstructive sleep apnea on H in patients. σ ($H_{baseline}$) = 0.1247 was obtained by H determinations on a group of healthy subjects who were breathing regularly. The difference in H during regular breathing and voluntary obstructive apnea, divided by 10 (because voluntary apneas may have induced larger changes than those experienced by patients) is $\Delta = (1.1627 - 0.2308) / 10 = 0.09319$. Thus, the estimated sample size for study A is 46.

Studies B and C are observational investigations on subjects referred for PSG as required by their medical condition and which fulfill the inclusion/exclusion criteria described previously. The number of subjects will be calculated accordingly to the results of the pre-study (group A).

Study D is an observational prospective investigation conducted on unselected consecutive patients without recruitment restrictions, in order to validate the KCG on the real population. Since we do not know how many patients will be necessary for the validation of our screening device, we speculate a size simple of 100 subjects.

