Because the KCG device is not intrusive, we do not anticipate difficulties in the recruitment. Our study will not affect in any manner the regular medical care of the patients admitted to the sleep laboratory. The present research proposal is in line with my promotor's expertise, [name], [name] and [name], in the study of sleep physiology (59-63), and sleep apnea (60, 61):

4. Perspectives

As explained above, SDB is a widespread disease with detrimental health effects and its prevalence is supposed to increase in the future years, as the result of the obesity pandemic in an ageing population. PSG is the gold standard for the diagnosis of sleep related disorders but it is an expensive, uncomfortable and time-consuming tool, limiting its use in the daily clinical practice, despite the high prevalence of SDB. Several home sleep tests have been proposed to screen patients suspected for SDB, but they disclose several limitations and are not recommended for patients with cardiovascular, respiratory, metabolic or neurologic co-morbidities (50). We strongly believe that the less cumbersome (57-60) KCG will screen patients for SDB accurately. One of its unique features (57-60) is also that it can directly identify the consequences of SDB and nCPAP therapy on the cardiovascular system, and in especially the presence of frequently associated cardiac arrhythmias (44). With a more efficient pre-screening, those who are most likely to be eligible for nCPAP therapy will have a better access to the currently existing sleep laboratory facilities. To summarize, we aim 1) to propose a new screening tool for patients at risk of SDB, 2) to stratify patients with SDB for adverse cardiovascular events, and 3) to highlight new physio-pathological aspect of sleep apnoea. The present research project has thus the potential of improving sleep apnoea patients care and health, at no additional societal costs.

5. References

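### Do the closing aims on cardiovascular risk stratification and on screening promise more than Groups A to D can deliver?

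*Protocol*

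**What the plan says.** Section 4 (Perspectives) of the protocol closes with three aims. The first is "1) to propose a new screening tool for patients at risk of SDB" and the second is "2) to stratify patients with SDB for adverse cardiovascular events". The third concerns new pathophysiological aspects of sleep apnoea. Just before this list, the section describes the intended use: "With a more efficient pre-screening, those who are most likely to be eligible for nCPAP therapy will have a better access" to sleep laboratories.

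Section 2 (Aims and hypothesis tested) is the formal statement. Its main hypothesis is that kino-cardiography (KCG) measures obstructive and central apnoea sensitively and accurately against PSG. It continues: "Our secondary hypotheses are related to modifications in the SCG and BCG parameters during the apnoea and the effects of nCPAP therapy". It mentions no cardiovascular event.

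The four groups are:
- **A:** "In 46 healthy volunteers, a computer program will generate random instructions of periods of normal breathing", with simulated apnoeas in between.
- **B:** selected patients with suspected sleep apnoea, with KCG and PSG recorded together.
- **C:** patients with diagnosed obstructive sleep apnoea, assessed for nCPAP efficacy under the same restrictions as B.
- **D:** 100 unselected consecutive patients "who will undergo PSG recordings because of complains of sleep apnoea".

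Section 3 (Methods) says Study D has no recruitment restrictions and is done "in order to validate the KCG on the real population". The background on sleep disordered breathing gives a prevalence of "up to 24% of men and to 9% of women aged 30 to 60 years" for asymptomatic, underdiagnosed disease.

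**The concern.** Two mismatches stand out.

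**Events.** Stratifying patients for adverse cardiovascular events requires observed events, or at least a validated measure of event risk. The groups have a laboratory session or sleep recordings, and no event definition or event follow-up. Groups B and C also exclude heart failure, permanent atrial fibrillation, frequent premature contractions and moderate or severe valve disease, so many of the patients most likely to have events are left out. Taken literally, the second aim cannot be met, and a later report might make a prognostic claim with no data behind it.

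**Screening population.** The protocol motivates KCG by the high prevalence of undetected disease in the general population and by pre-screening ahead of the sleep laboratory. Every Group D patient has already reached that laboratory with complaints. If disease is much more common there, predictive values observed in Group D would flatter a positive screen in people not yet referred.

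**Working it through.** **The plan's own figure.** The only calculated sample size is Study A's:

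2 × (1.96 + 1.64)² × 0.1247² / 0.09319² = 46.41, against the stated 46.

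It reproduces. It concerns the signal ratio H and has no bearing on events or screening.

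**Step 1: does anything in the plan depend on the event aim?**

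| Element | Content | Depends on events? |
|---|---|---|
| Main hypotheses (section 2) | Apnoea detection against computer-generated apnoeas (A) or PSG (B, C, D) | No |
| Secondary hypotheses (section 2) | PEP, LVET, IVRT, R-J, heart rate variability, breathing effort, nCPAP effect | No |
| Sample size A | H during apnoea against regular breathing | No |
| Sample size B, C | To follow from the results of A | No |
| Sample size D | 100, a working figure | No |
| Eligibility | Signal reliability in B and C; none in D | No |

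Removing the item from section 4 would leave every row as it is.

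**Step 2: would adding event follow-up be a worthwhile remedy?** The protocol gives no event rate or hazard ratio, so all inputs here are assumptions: two-sided 5%, power 80%, patients split equally into two risk groups. Required events = 4 × (1.96 + 0.84)² / (ln HR)².
- HR 1.5: 191 events
- HR 2: 66 events
- HR 3: 27 events

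With 100 patients and an assumed yearly event rate of 2% to 10%, one year gives about 2 to 10 events. Three years give 100 × (1 − 0.98³) = 6 to 100 × (1 − 0.90³) = 27. For HR 2, power is about 7% with 2 events and 44% with 27. Follow-up of Group D would be a different and underpowered study.

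**Step 3: how far do predictive values move with prevalence?**

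PPV = se·p / [se·p + (1 − sp)(1 − p)]

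NPV = sp(1 − p) / [sp(1 − p) + (1 − se)p]

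Inputs: 24% and 9% are the protocol's background figures. The 70% referral prevalence and the 90%/80% accuracy are assumed. The 98%/94% pair is what the background reports for an earlier ballistocardiography study; it concerns detection of breathing events, so using it for whole patients is only illustrative.

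| Prevalence | PPV (90%/80%) | NPV (90%/80%) | PPV (98%/94%) |
|---|---|---|---|
| 70% | 0.63/0.69 = 0.913 | 0.24/0.31 = 0.774 | 0.974 |
| 24% | 0.216/0.368 = 0.587 | 0.608/0.632 = 0.962 | 0.838 |
| 9% | 0.081/0.263 = 0.308 | 0.728/0.737 = 0.988 | 0.618 |

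Varying the assumed referral prevalence from 60% to 80% gives a PPV of 0.87 to 0.95 with the 90%/80% pair.

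**Step 4: does the protocol plan to use those quantities?** It speaks of sensitivity and specificity when tuning the signal for Group A, of sensitive and accurate measures against PSG, and of Bland-Altman agreement in Group B. Positive and negative predictive values appear nowhere.

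**Step 5: what does the Study D wording mean in context?** Groups B and C exclude patients whose heart rhythm, drugs or comorbidities could spoil the signal. Study D removes those exclusions, and the Group D paragraph in section 2 gives the purpose as usefulness in patients with several comorbidities. The contrast is between selected and unselected sleep-test patients. The same paragraph states the referral basis openly, and the screening aim in section 4 names patients at risk, not the general population.

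**The case for a change.** The strongest case for a change rests on the wording of section 4. It says these are aims, not future possibilities. The event item stands between two that the groups do address, so an ethics committee or funder cannot tell that this one alone is aspirational. Nor can an analysis plan rescue it, because no plan can analyse an outcome that was never collected. On screening, section 4 places KCG ahead of the sleep laboratory, while every Group D patient is already inside it. Group D therefore does not test that pre-referral use.

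Part of this stands. Sections 2 and 4 do not match on events, and the study will yield no estimate of event risk. Group D results also need a generalisability caveat: predictive values would not carry over to unreferred people, and sensitivity and specificity may shift too if referred patients have more marked disease.

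It does not follow that the plan is defective. The mismatch lies between a closing outlook and a formal aims section, and the formal section governs the hypotheses and groups. It is also not shown that disease is far commoner in Group D than in the intended users. The protocol gives no prevalence for referrals or for at-risk patients, and its 24% and 9% are upper figures for asymptomatic disease.

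**Conclusion.** No change to the plan follows. On events, the observation is correct: zero events are collected. But no hypothesis, sample size or analysis needs them, so the item reads as an ambition beyond this study. Labelling it as future work would be a tidy wording correction and would affect no result. On screening, the claim that the aim cannot be met fails, because Group D can estimate accuracy against PSG in unselected patients with sleep-apnoea complaints, who fall within the stated at-risk target. The phrase in section 3 is loose but clear beside the restrictions on B and C.

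The fall in positive predictive value from 0.91 to 0.59 or 0.31 is arithmetically right under the assumed 90% sensitivity, 80% specificity and 70% referral prevalence. It concerns a quantity the protocol does not plan to report, and how predictive values are presented is properly left to the analysis plan or the report. This conclusion assumes that section 2 is the operative statement of aims, and that the report makes no claim on cardiovascular event risk or on performance in unreferred people.
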